2.6 Analysis of the key secondary objectives

2.6.1 Key secondary endpoints

2.6.1.1 Disability worsening (3-month or 6-month confirmed)

A 3-month confirmed disability worsening (3mCDW) is defined as an increase from baseline in EDSS sustained for at least 3 months. Analogously, a 6-month confirmed disability worsening (6mCDW) is defined as an increase from baseline in EDSS sustained for at least 6 months. This means that after a scheduled or unscheduled visit at which the patient fulfills the disability worsening criterion as defined in [Table 2-13](#), all EDSS assessments (scheduled or unscheduled) need to also fulfill the worsening criteria until the worsening ("the event") can be confirmed at the first scheduled visit that occurs in the absence of (confirmed or unconfirmed) relapse 3 months/90 days (or 6 months/166 days) after the onset of the worsening, or later.

In the time to event (3mCDW or 6mCDW) analysis, time will be calculated as (the date of EDSS assessment at onset of the event – date of first administration of study drug+1) for patients with the events. Censoring occurs in those patients who did not experience an event in the study (during the treatment epoch), this includes patients who had a "tentative" disability worsening that could not be confirmed due to an early discontinuation or any another reason. The censoring time is calculated as (the date of last EDSS assessment during the treatment epoch – date of first administration of study drug+1). Additional details are provided in footnote of Table 2-13.

Table 2-13 Criterion for disability worsening based on change in EDSS score

Total EDSS at baseline*	"Disability worsening" criterion
0	$\geq +1.5$

0.5 to 5	$\geq +1$
≥ 5.5	$\geq +0.5$

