
A 3-month confirmed disability worsening can have an onset at any scheduled or unscheduled visit if the disability worsening criterion is met. A disability worsening can only be confirmed at a scheduled visit in the absence of (confirmed or unconfirmed) relapse if, over a period of 3 months (≥ 90 days=3×30) time interval, all assessments meet the worsening criterion.
 
A 6-month confirmed disability worsening can have an onset at any scheduled or unscheduled visit if the disability worsening criterion is met. A disability worsening event can only be confirmed at a scheduled visit in the absence of (confirmed or unconfirmed) relapse if, over a period of 6 months (≥ 166 days=$6 \times 30 - 14$ [visit window]) time interval, all assessments meet the worsening criterion.
 
If a patients dies due to MS (EDSS=10 at any time), it will be considered a confirmed disability worsening regardless of the baseline EDSS or the change in EDSS. The time will be calculated as (date of EDSS assessment at a tentative onset of the event – date of first administration of study drug+1) or (date of death – date of first administration of study drug + 1) if a tentative onset date does not exist. Note: Death for other reasons than MS (i.e. not EDSS=10) will not be considered a disability worsening.
 
*Baseline EDSS is defined as the last EDSS assessment prior to the first dose of study medication (protocol inclusion criterion is EDSS 0-5.5)
	

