- Time to 6-month confirmed worsening of at least 20% in the timed 25-foot walk test (T25FW): similar to definition of 6mCDW ([Section 2.6.1.1](#)) but replacing the worsening criteria by at least 20% increase from baseline in T25FW score. Patients who do not reach the endpoint by the end of treatment epoch date will be censored at date of last T25FW assessment during the treatment epoch.
- Time to 6-month confirmed worsening of at least 20% in the 9-Hole Peg Test (9HPT): similar to definition of 6mCDW ([Section 2.6.1.1](#)) but replacing the worsening criteria by at least 20% increase from baseline in 9HPT score in at least one hand. Patients who do not reach the endpoint by the end of treatment epoch date will be censored at date of last 9HPT assessment during the treatment epoch.

- 6mCDI sustained until EOS: same as 6mCDI except that the rest EDSS scores (scheduled or unscheduled) after the confirmation visit of the 6mCDI during the treatment epoch have to meet the disability improvement criteria as well.
- Disability status during the study (classified as improved, stable, or worsened): patients will be classified as improved if 6mCDI sustained until EOS was met (regardless whether 6mCDW status was met at an earlier time point); or classified as stable if 6mCDW was not met & 6mCDI sustained until EOS was not met; or classified as worsened if 6mCDW was met & 6mCDI sustained until EOS was not met.
- MS relapse characteristics include severity, recovery, hospitalization, and steroid treatment. The severity of MS relapses will be derived according to the criteria in [Table 2-15](#). All relapses (confirmed or unconfirmed) will be considered. For confirmed relapses, the EDSS used to confirm the relapse (as specified in [Section 2.5.2](#)) will be used to determine the severity. For unconfirmed relapses, all EDSS assessments taken within 30 days from the relapse start date and before the relapse end date will be checked among which the most severe case will be selected to determine the severity. If no such EDSS assessment is available, the severity will be set to “missing EDSS”. If none of such EDSS assessments meet the mild, moderate or severe conditions, the severity will be set to “no worsening in EDSS”.

Table 2-15 Severity of MS relapse

Mild relapse	Moderate relapse	Severe relapse
EDSS increase of 0.5 point	EDSS increase of 1 or 2 points	Exceeding Moderate criteria
or	or	or

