- Annualized rate of brain atrophy (ARBA) by visit-window: ARBA describes the “averaged annual percentage change” in brain volume. It is designed to adjust for differences in the time spent between two scans that are compared by standardizing the percentage change in brain volume (PBVC) to 1 year. The logic of interest rates applies. $ARBA = [(PBVC/100+1)^{(365.25/days)}-1]*100$, where “PBVC” represents the percentage brain volume change obtained between 2 scans and “days” stands for the number of days between the two scans that are being compared. Days are calculated as post-baseline MRI scan date – screening MRI scan date +1.
- Proportion of patients free of clinical and MRI disease activity (No evidence of disease activity; NEDA-4): NEDA-4 is defined as no 3mCDW, no confirmed MS relapse, no new or enlarging T2 lesions on any MRI scan (scheduled or unscheduled) compared to baseline, and brain volume change $>-0.4\%/year$ on all MRI scans (scheduled and unscheduled; brain volume as measured by ARBA). The main analysis will consider only those patients who were followed-up to the assessment time point in the analysis (e.g. only patients with ≥ 12 months of follow-up in the 12-month assessment of disease freedom, etc.). Intermediate missing values (e.g. due to missing MRI assessments) will be considered not free of disease activity. For the derivation of NEDA-4, data up to day 365.25 will be considered in the year 1 analysis and data up to day 730.5 will be considered in the year 2 analysis.
- EDSS total score by visit-window
- The 25-foot Timed Walking Test (T25FW) score by visit-window: two trials will be performed at each scheduled visit. The average scores of the two trials per visit will be calculated as $T25FW_{score} = \frac{1}{2}(T25FW_1 + T25FW_2)$. In case of missing data, the average of the non-missing values will be taken.
- The 9-Hole Peg Test (9HPT) score by visit-window: four trials (two of each arm) will be performed at each scheduled visit. The 9HPT score per visit will be calculated for the dominant and the non-dominant hands separately and then for the average of both hands. In case of missing data, the average of the non-missing values will be taken.
 - $9HPT_{dominant\ hand} = (9HPT_{dominant\ hand, trial\ 1} + 9HPT_{dominant\ hand, trial\ 2})/2$
 - $9HPT_{non-dominant\ hand} = (9HPT_{non-dominant\ hand, trial\ 1} + 9HPT_{non-dominant\ hand, trial\ 2})/2$
 - $9HPT_{total} = (9HPT_{non-dominant\ hand} + 9HPT_{dominant\ hand})/2$.

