2.7.3 Handling of missing values/censoring/discontinuations

As a general rule, missing data will not be imputed in any secondary endpoint analyses. All the available data up to the end of treatment epoch date, irrespective of on or off study treatment will be used as applicable. Details of handling discontinuations or censoring are provided in the relevant endpoints or analysis of endpoints sections ([Section 2.7.1](#) and/or [Section 2.7.2](#)).

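### The SAP has no rule for a patient who cannot complete the T25FW or 9HPT because of MS, so by default that patient is censored unless the worsening is confirmed some other way

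*SAP*

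**What the plan says.** SAP 2.7.1 builds both endpoints on the 6mCDW definition in SAP 2.6.1.1 and changes only the criterion: "replacing the worsening criteria by at least 20% increase from baseline in T25FW score", and "replacing the worsening criteria by at least 20% increase from baseline in 9HPT score in at least one hand". Patients without an event are censored. For the walk: "Patients who do not reach the endpoint by the end of treatment epoch date will be censored at date of last T25FW assessment". For the peg test, the patient "will be censored at date of last 9HPT assessment during the treatment epoch".

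The scores are averages of timed trials: two for the walk, two per hand for the peg test, and then both hands for the 9HPT total. Where trials are missing, SAP 2.7.1 says: "In case of missing data, the average of the non-missing values will be taken". SAP 2.7.3 adds: "As a general rule, missing data will not be imputed in any secondary endpoint analyses".

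The borrowed definition in SAP 2.6.1.1 censors a tentative "disability worsening that could not be confirmed due to an early discontinuation or any another reason". Its one provision for an extreme outcome is in the footnote to Table 2-13: "If a patients dies due to MS (EDSS=10 at any time), it will be considered a confirmed disability worsening".

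Protocol 6.4.5 and 6.4.6 describe both tests as times in seconds. Neither document gives a maximum time, a code or a scoring rule for a patient who cannot finish. Protocol 6.4 leaves administration details to site manuals, which are not part of these documents.

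**The concern.** Inability to walk 25 feet, or to finish the pegs with one hand, is a worse result than a 20% slower time, but it produces no time. If it is handled as an absent value, the patient leaves the risk set because of the event being studied. The Cox models in SAP 2.7.2 assume that censoring carries no such information.

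The visit-wise summaries are affected too. A walk with one failed trial is scored on the trial that succeeded. A 9HPT total with one hand lost is scored on the hand that still works, so a severe loss can read as stability.

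At stake are the interpretation of two time-to-worsening endpoints and the T25FW and 9HPT means. If the plan stays silent, the choice falls to whoever programs the derivation.

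**Working it through.** **1. Following one patient through the rules.** Suppose MS removes the ability to do the test at some visit.

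- *Is there a score?* If no trial is completed, there is nothing to average and nothing is imputed (SAP 2.7.1, 2.7.3). If one trial is completed, it becomes the score.
- *Was a 20% worsening already confirmed?* Then the event stands.
- *Was a 20% worsening seen but not confirmed?* SAP 2.6.1.1 confirms at the first scheduled visit at least 166 days after onset, or later, if all assessments in between qualify. A visit without a value does not break the chain, so a later completed test can still confirm. Without one, the patient is censored.
- *No 20% worsening seen?* Censored at the last completed test.
- *9HPT only:* the other hand can still produce an event.

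The peg test has little slack. Protocol Table 6-1 schedules it at Months 6, 12, 18 and 24 plus EOT/EOS, and a study month is 28 days, so consecutive visits are nominally 6 × 28 = 168 days apart, against the 166 required. Confirmation normally rests on the single next visit. The walk is measured every 3 months.

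For the 9HPT total, write A and B for the two hand scores. The total is (A + B)/2. If B cannot be obtained, averaging the non-missing values gives A, and the lost hand disappears from the summary.

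**2. Anchor.** The documents give no event count, power or frequency of inability for these endpoints. The 6mCDW target is used only to set a scale. SAP 3.1.7: hazard ratio (HR) 0.614, 80% power, one-sided alpha 0.025 − 0.025² = 0.024375, 133 events. Schoenfeld's formula, d = 4(z₁₋α + z_power)²/(ln HR)², gives 133, which reproduces the stated figure.

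**3. Illustration on assumed losses.** Let f_ofa and f_ter be the fractions of true events turned into censorings in each arm. With rare events, observed HR ≈ 0.614 × (1 − f_ofa)/(1 − f_ter). Ofatumumab's share of events is 0.614/1.614 = 0.380, so remaining events d = 133 × [0.380(1 − f_ofa) + 0.620(1 − f_ter)]. Power at two-sided 0.05 is Φ(√d/2 × |ln HR| − 1.96).

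| Lost, ofatumumab / teriflunomide (assumed) | HR | Events | Power |
|---|---|---|---|
| 0% / 0% | 0.614 | 133 | 80.3% |
| 2% / 2% | 0.614 | 130.3 | 79.5% |
| 5% / 5% | 0.614 | 126.3 | 78.3% |
| 10% / 10% | 0.614 | 119.7 | 76.1% |
| 20% / 20% | 0.614 | 106.4 | 71.1% |
| 0% / 5% | 0.646 | 128.9 | 69.8% |
| 5% / 10% | 0.648 | 122.2 | 66.9% |
| 5% / 20% | 0.729 | 114.0 | 39.2% |
| 10% / 5% | 0.582 | 123.8 | 85.4% |

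Equal fractions leave the HR alone and cost power. Unequal fractions move it, and the last row moves it in ofatumumab's favour.

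**The case against.** The strongest reply is that this is silence, not a rule. A reader might infer that the SAP declares inability to be missing data. It does not: no text says whether a failed attempt is an assessment, a missing value or a coded one, and the site manuals might assign a time. That stands, and it is why the point is put as a missing rule with a default consequence. It does not dispose of the point, because an endpoint derivation belongs in the SAP.

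It is also tempting to say that any worsening followed by inability is lost. That is too absolute, given the routes to an event shown above.

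Nor is the MS-death provision good evidence of inconsistency with the EDSS endpoint. It concerns death, not a failed test, and is arguably inherited, since both definitions borrow from 2.6.1.1.

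Finally, entry EDSS is 0 to 5.5 and treatment lasts at most 30 months, so cases may be few. Loss of walking is also captured by the EDSS, which includes an ambulation score and feeds the multiplicity-controlled 3mCDW and 6mCDW endpoints. Both points limit the size of the problem; neither supplies the missing rule.

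**Conclusion.** The gap is real for both endpoints. As written, the rules lead by default to outcome-driven censoring, and to visit scores that rest on what the patient could still do. It should be corrected, but it does not touch the primary or key secondary conclusions: both endpoints lie outside the testing procedure in SAP 2.5.3, and no End of Study criterion uses them.

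Two stronger readings are not supported. A reader might infer bias toward no difference because the arm with more worsening loses more patients. A larger number lost does not shift the hazard ratio; a larger fraction does, and the documents do not say which arm would lose the larger fraction.

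A reader might also put a figure on the loss. Assuming that 0.5–2% of patients lose the ability and 10–15% have a confirmed worsening gives 0.5/15 = 3% to 2/10 = 20% of events. Neither input is in the documents, and the ratio supposes that none of these patients had an earlier confirmed event. The table above is likewise an illustration on assumed losses, not an estimate.

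**What to change.** In SAP 2.7.1, before unblinding, state that a scheduled T25FW, or a scheduled 9HPT for a given hand, not completed because of MS-related inability meets the 20% worsening criterion at that visit, for both onset and confirmation. Base this on the recorded reason. Tests missed for any other reason stay missing.

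Report the number of patients with such inability by arm and test, and repeat both Cox analyses under the SAP's present censoring rule as a sensitivity analysis.

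For the visit-wise summaries, do not compute a 9HPT total from one hand when the other could not complete because of MS; report those patients separately. No substitute score is proposed for a visit with one completed and one failed trial, so the measured time stands.

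The cost is a few sentences in the SAP, one extra run per endpoint, and a reason-not-done field, which must exist or be added to the CRF. The downside is that the site has to judge the reason. The SAP's change log already records an addendum after database lock. If treatment codes are open by the time this is acted on, leave the main definition alone, and give the counts by arm and the inability rule as a labelled sensitivity analysis.

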2.2 Secondary objective(s)

Key secondary objectives

All disability-related key-secondary objectives will be addressed in the combined data (meta-analysis) from this study and the second study of identical design. All other objectives will be addressed based on the data from this study alone.

The key secondary objectives are to evaluate if ofatumumab 20 mg sc q4 weeks is superior to teriflunomide 14 mg po once daily on the following efficacy measures:

- Time to disability worsening as measured by 3-month confirmed worsening (3mCDW) on The Expanded Disability Status Scale (EDSS)
- Time to disability worsening as measured by 6-month confirmed worsening (6mCDW) on EDSS
- Time to disability improvement as measured by 6-month confirmed improvement (6mCDI) on EDSS
- Number of T1 Gd-enhancing lesions per MRI scan
- Number of new or enlarging T2 lesions on MRI per year (annualized T2 lesion rate)
- Neurofilament light chain (NfL) concentration in serum
- Rate of brain volume loss (BVL) based on assessments of percentage brain volume change from baseline

Other secondary objectives

Evaluate if ofatumumab 20 mg sc q4 weeks is superior to teriflunomide 14 mg po once daily on the following efficacy measures:

- Time to first relapse
- Annualized relapse rates > 8 weeks after the onset of treatment
- Risk of a 3mCDW > 8 weeks after the onset of treatment
- Risk of a 6mCDW > 8 weeks after the onset of treatment
- Time to a 6-month confirmed cognitive decline (6mCCD), defined as a 4-point worsening on Symbol Digit Modalities Test (SDMT)
- Time to 6mCDW or 6mCCD, whichever is reached first
- Change in cognitive performance relative to baseline as measured by the SDMT
- Time to 6-month confirmed worsening of at least 20% in the timed 25-foot walk test (T25FW)
- Time to 6-month confirmed worsening of at least 20% in the 9-hole peg test (9HPT)
- Time to 6mCDI sustained until End of Study (EOS) as measured by EDSS
- Number of new or enlarging T2 lesions between Month 12 and EOS
- Change in T2 lesion volume relative to baseline
- Proportion of patients with no evidence of disease activity (NEDA-4; defined in [Section 9.5.1.2](#)) at year 1 and 2
- Physical and psychological impact of MS disease as measured by the Multiple Sclerosis Impact Scale (MSIS-29)

[figure not shown]
In the subgroup of newly diagnosed, treatment-naïve patients, evaluate if:

- High NfL (above median) concentration at baseline is predictive of higher disease activity post baseline

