9.5.1.2 Other secondary efficacy variables

- The analysis of “Time of first relapse” and “Annualized relapse rates > 8 weeks after the onset of treatment” is described in (Section 9.4.3) as sensitivity analysis to the primary analysis.

- The analysis of the “Risk of a 3mCDW > 8 weeks after the onset of treatment” and “Risk of a 6mCDW > 8 weeks after the onset of treatment” is described in ([Section 9.5.1.1.1](#)) as a supportive analysis to the key-secondary 3mCDW and the 6mCDW, respectively.
- Time to 6mCCD will be analyzed in the combined FAS from studies COMB157G2301 and COMB157G2302, in a Cox proportional hazards model with study as stratum, treatment and region as factors, and baseline SDMT as continuous covariates.
- Time to 6mCDW or a 6mCCD, whichever is reached first, will be analyzed in the combined FAS from studies COMB157G2301 and COMB157G2302, in a Cox proportional hazards model with study as stratum, treatment and region as factors, and baseline EDSS and baseline SDMT as continuous covariates.
- SDMT scores and change from baseline will be summarized by visit and by treatment. The change from baseline will be analyzed and compared between treatments in a repeated measures mixed effects model.
- Time to 6-month confirmed worsening of at least 20% in the timed 25-foot walk test (T25FW) will be analyzed in the combined FAS from studies COMB157G2302 and COMB157G2301, in a Cox proportional hazards model with study as stratum, treatment, and region as factors and the baseline T25FW-result as a continuous covariate. The baseline 25TWT-result is defined as the last assessment prior to the first dose of study medication; the 20% worsening is defined relative to this reference value.
- Time to 6-month confirmed worsening of at least 20% in the 9-hole peg test (9HPT) will be analyzed in the combined FAS from studies COMB157G2302 and COMB157G2301, in a Cox proportional hazards model with study as stratum, treatment, and region as factors and baseline 9HPT-result as a continuous covariate. The baseline 9HPT-result is defined as the last assessment prior to the first dose of study medication; the 20% worsening is defined relative to this reference value.
- Change in T2 lesion volume on MRI will be summarized by visit. Cross-sectional analyzes will be done by using a rank ANCOVA with treatment and region (factors), and baseline T2 volume as a continuous covariate.

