2.1.2 Visit windows

2.1.2.1 Visit windows for treatment epoch

Visit-windows will be used for both efficacy and safety data summaries by visit. Visit windows define a time period “around” the targeted visit date as defined in the evaluation schedule of the clinical study protocol. Visit-windows are non-overlapping, and defined without gaps between consecutive visit windows. The width of visit windows may vary over the course of the study period.

Baseline assessments are defined in [Section 2.1.1](#) and do not require a visit window.

The purpose of visit windows is to analyze data based on the actual study days (rather than "nominal" visits). E.g., if a patient’s Month 1 visit is delayed; it is possible that the Month 1 data be re-aligned to visit-window Month 2 and be summarized under Month 2.

- For **efficacy analyses** (including PK concentration by visit analysis) all nominal visits (i.e. excluding unscheduled visits) will be mapped into one of the defined visit-windows. Note: for the derivation of disability worsening or improvement all visits (scheduled and unscheduled) need to be considered before the worsening or improvement can be confirmed (see [Section 2.6.1.1](#)). Similarly, for No Evidence of Disease Activity (NEDA-4), all visits (scheduled and unscheduled) need to be considered ([Section 2.7.1](#)).

-For **safety analyses** all visits (scheduled and unscheduled) will be mapped to visit windows. Safety data from unscheduled visits may be reported separately if applicable.

It is possible that more than one assessment of a patient fall into a particular visit-window. [Section 2.1.2.3](#) deals with the statistical approaches to handle multiple visits in a given visit-window.

Tables displaying summary statistics “by visit” will also use the term *visit-window* as column header; this is to remind the reviewer that multiple assessments of a patient might be summarized. Below tables provide visit-windows definitions for applicable parameters.

Table 2-3 Visit-windows for EDSS*/T25FW

Visit-window	Start day	Target Day	End day
Week 12	1	84	126
Week 24	127	168	210
Week 36	211	252	294
Week 48	295	336	378
Week 60	379	420	462
Week 72	463	504	546
Week 84	547	588	630
Week 96	631	672	714
Week 108	715	756	798
Week 120	799	840	881

* For EDSS, assessment on Day 1 will be excluded as baseline EDSS can occur on Day 1 per protocol.

Table 2-4 Visit-windows for 9HPT/SDMT/MSIS-29/

Visit-window	Start day	Target Day	End day
Week 24	1	168	252

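### Confirmed 9HPT worsening is tested visit by visit in either hand, so as written one hand can start the event and the other confirm it

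*SAP*

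**What the plan says.** SAP 2.7.1 defines the 9HPT event by analogy with 6mCDW, "replacing the worsening criteria by at least 20% increase from baseline in 9HPT score in at least one hand".

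The algorithm it borrows is in SAP 2.6.1.1. After onset, "all EDSS assessments (scheduled or unscheduled) need to also fulfill the worsening criteria until the worsening" can be confirmed. Confirmation takes place at a scheduled, relapse-free visit at least 166 days after onset. The footnote to Table 2-13 repeats the rule: over the "time interval, all assessments meet the worsening criterion".

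Further down in SAP 2.7.1, under the score by visit window: "The 9HPT score per visit will be calculated for the dominant and the non-dominant hands separately and then for the average of both hands". Hand-level scores therefore exist in the analysis data.

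The protocol does not settle the matter. The objective in section 2.2 names no hand, and section 9.5.1.2 refers to one result: "The baseline 9HPT-result is defined as the last assessment prior to the first dose of study medication". Neither document says that onset and confirmation must be in the same hand.

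**The concern.** In 6mCDW the criterion applies to one score, the EDSS total, and that score has to stay raised. Once the criterion becomes a 20% increase in either hand, the test at each visit is whether the worse hand is over the threshold. Two different hands can then satisfy it on two occasions, and no single score has to stay raised.

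Confirmation exists to screen out transient readings. If a transient reading in one hand can be confirmed by a transient reading in the other, part of that protection is lost. The extra events would tend to be noise. If they are unrelated to treatment, they add similar event rates to both arms and tend to pull the hazard ratio toward 1. Two programmers working from this text could also arrive at different event counts.

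**Working it through.** The plan gives no sample size, event rate or reliability figure for 9HPT worsening, so there is no stated figure to reproduce. The check has two parts.

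**1. Does the rule as written confirm an alternating-hand patient?**

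- Schedule: Protocol Table 6-1 has 9HPT at Months 6, 12, 18 and 24 and at EOT/EOS. SAP Table 2-4 ("Visit-windows for 9HPT/SDMT/MSIS-29") puts the Month 6 and Month 12 targets at Days 168 and 336.
- Gap: 336 − 168 = 168 days, which meets the 166-day requirement. Two adjacent on-schedule visits are enough, with no scheduled 9HPT between them.
- Example: Month 6, hand A +25% and hand B +5%; Month 12, hand A +5% and hand B +25%.
- As written: the larger change is +25% at both visits, so the event is confirmed.
- Same hand required: hand A fails at Month 12 and hand B fails at Month 6, so there is no event.

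**2. How many false events could this add?**

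Assumed input: p, the chance that a stable hand reads at least 20% slow at a visit, set at 2%, 5% and 10%. Errors are first taken as independent across hands and visits. An event means that the criterion is met at two consecutive visits. Three visits (Months 6, 12 and 18) are used because Protocol 9.8.1.1 expects most patients to be exposed for 1 to 2 years.

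- Either hand: q = 1 − (1 − p)²; false-event probability = 2q² − q³.
- Same hand: r = 2p² − p³ for each hand; false-event probability = 1 − (1 − r)².

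For p = 5%: q = 0.0975, so 2(0.009506) − 0.000927 = 0.01809. For the same hand, r = 0.005 − 0.000125 = 0.004875, so 1 − (0.995125)² = 0.00973.

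| p | Same hand | Either hand |
|---|---|---|
| 2% | 0.16% | 0.31% |
| 5% | 0.97% | 1.81% |
| 10% | 3.8% | 6.5% |

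**Sensitivity to these assumptions**

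- *Five visits.* This needs the 30-month maximum. The figures become 0.31% against 0.61%, 1.91% against 3.52%, and 7.25% against 12.28%.
- *166-day gap missed.* Visit windows of ±14 days can bring an adjacent pair below 166 days, and a further qualifying visit is then needed. For one run of three qualifying visits the formulas are 1 − (1 − p³)² and q³. They give 0.0016% against 0.0062%, 0.025% against 0.093%, and 0.20% against 0.69%. The table above ignores this and so overstates the absolute rates.
- *Correlated errors.* Each hand is always compared with its one baseline reading, so its errors are shared across visits. In simulation (400,000 stable patients per scenario, five visits, between-hand correlation 0 or 0.5), between-visit correlation of 0.3 to 0.5 reduced the relative rise to about 8 to 23%. Repeating it with three visits gave a similar range.

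Every same-hand event is also an either-hand event, so the literal rule can only add events.

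**The case against.** **The SAP may intend a per-hand rule.** SAP 2.6.1.1 opens by describing a sustained increase. Carried over, that could mean an increase in one hand that is itself sustained, and the hand-level scores needed to program this exist. The reading is possible. However, the same section goes on to spell out what sustained means, namely that every assessment meets the criterion, and the criterion supplied is either hand. The ambiguity stands. A reader might infer that the SAP deliberately allows a switch of hands; it does not say so, it is silent.

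**6mCDW does not require the same functional system at onset and confirmation, so why match hands?** The analogy fails because in 6mCDW one score, the EDSS total, has to remain raised. Here no single score does.

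**The size is assumption-driven.** This is right. The 2 to 10% range has no source in the documents, independence is the least favourable case in relative terms, and five visits would suit only patients followed to the maximum.

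**The harm is not shown.** A reader might infer a material bias in the 9HPT hazard ratio. No hazard-ratio, event-count or power calculation supports that, and the documents give no 9HPT event rate to set the false events against. The same rule applies in both blinded arms and the expected direction is conservative, so no false claim of benefit is shown.

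**It is a minor endpoint.** Also right: it is an other-secondary objective outside the testing procedure in SAP 2.5.3.

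**Conclusion.** The gap in the definition is real. Applied literally, SAP 2.7.1 with 2.6.1.1 confirms a patient in whom neither hand worsened for 6 months, and this can happen on the planned schedule.

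How often it would happen is unknown. Under the assumptions in the table, the either-hand rule adds about 0.15 percentage points of false events at p = 2% (0.31 − 0.16), 0.84 at 5% (1.81 − 0.97) and 2.7 at 10% (6.5 − 3.8). The relative rise is large only if errors are independent between visits. Dilution of the hazard ratio is a reasonable expectation if the extra events are unrelated to treatment, but it has not been quantified.

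The point does not reach the primary or key secondary results, and the documents give no basis for saying that it does. It is worth correcting because this is a named superiority objective analysed in the pooled FAS, and its event definition should give one answer.

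**What to change.** Define the event per hand in SAP 2.7.1: the same hand must be at least 20% above its own baseline at onset, at every assessment in between and at the confirming scheduled visit. The event time is the earlier confirmed onset of the two hands. In the same edit, say which 9HPT score (one hand or the average) is the baseline covariate in the Cox model of SAP 2.7.2, which is also left open.

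The cost is a sentence or two and a small programming change. No new data are needed, and a few events that are probably noise are lost. If the analysis has already been programmed, state which derivation was used and report the other as a sensitivity analysis.
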